8.6 Safety

The methods, assessment, specification, and recording for each assessment will be detailed in the Site Operations Manual.

8.6.1 Physical examination

A complete physical examination will be performed at the visits indicated in the [Assessments schedule](#) (Table 8-1) and will include an assessment of skin, head and neck, lymph nodes, heart, lungs, abdomen, back, neurological function and comments on general appearance. All significant findings that are present prior to signing informed consent must be reported on the relevant medical history/current medical conditions eCRF. Significant findings made after signing the informed consent that meet the definition of an AE and must be recorded on the adverse events eCRF. Due to the seriousness of the illness at baseline it might not be possible to assess all aspects of physical examination.

8.6.2 Vital signs

Vital signs will include pulse rate, systolic and diastolic blood pressure in supine position, respiratory rate, and temperature which will be assessed at the visits indicated in [Table 8-1](#).

8.6.3 Clinical laboratory evaluations

Due to the emergency setting of the patient, screening/baseline laboratory evaluation can be performed locally. A central laboratory will be used for all other time points for the analysis of all specimens collected. Timings of blood sample collection are outlined in the [Table 8-1](#). Details on the collections, shipment of samples and reporting of results by the central laboratory are provided to investigators in the laboratory manual. Abnormal laboratory parameters, inconsistent with clinical presentation of stroke or which cause suspicion of an underlying medical condition, should be repeated for confirmation. Additional local lab samples will be taken according to the site's local practice to adhere to local standard of care for ICH patients.

8.6.3.1 Hematology

Blood samples will be collected at the scheduled visits indicated in [Table 8-1](#). The parameters assessed will include: red blood cell count, total and differential WBC count (basophils, eosinophils, lymphocytes, monocytes, neutrophils), platelet count, hemoglobin, hematocrit,

mean corpuscular volume, mean corpuscular hemoglobin, mean corpuscular hemoglobin concentration and red blood cell morphology.

Due to the seriousness of the condition, local lab blood sampling needed for the routine medical care will have to be taken as well. **The Treating Physician will take special care that after the initiation of study treatment absolute total WBC count and lymphocyte counts are only communicated to persons on the treatment team who need to know this result for clinical decision making.** It is imperative that this information is not communicated more broadly: the Treating Physician must under no circumstances communicate this information to ward personnel, and particularly not to local Independent Raters, those study team members who will be conducting follow-up mRS assessments on ICH patients.

For study blinding purposes after the baseline visit only the absolute counts for eosinophils, basophils, neutrophils and monocytes will be communicated to sites by the central laboratory. The absolute total WBC, and lymphocyte counts will be measured at each visit by the central laboratory, will be blinded from the sponsor and the Investigator; and will **only** be communicated to the site Principal Investigator in case of an abnormality which might require an AE evaluation and/or could result in a change in patient treatment.

8.6.3.2 Clinical chemistry

Blood samples will be collected at the scheduled visits indicated in [Table 8-1](#) and the parameters assessed will include: electrolytes (Na, K, Cl, bicarbonate, Ca, Mg, P), non-fasting glucose, albumin, alkaline phosphatase, creatinine, ALT, AST, GGT, amylase, total bilirubin, conjugated bilirubin, and CRP. After the initial screening chemistry, total cholesterol, triglycerides, HDL, and LDL may or may not be repeated at the discretion of the Investigator.

8.6.4 Electrocardiogram (ECG)

Continuous cardiac monitoring must be implemented via bedside monitoring or telemetry in all patients during days when the patient is in the Stroke Unit/Neurointensive Care Unit. Cardiac monitoring must be performed from 1 hour before dosing to 48 hours after the first drug administration. Continuous cardiac monitoring may be done for a longer duration on a case-by-case basis at the discretion of the Investigator and the treating physician.

Standard twelve-lead ECGs will be performed for all patients at the time points as indicated in [Table 8-1](#). All ECG data must be stored and made available to the sponsor upon request.

For telemetry, in the event of clinical significant abnormalities, rhythm strips should be captured and printed, or annotated by the Investigator/treating physician, and kept with the source documents. In the case of no CV abnormalities, source notes confirming review of telemetry data are sufficient. Cardiac safety monitoring data will be used for cardiac rhythm evaluation (mainly bradyarrhythmias, such as atrioventricular blocks and sinus pauses) and for HR assessments.

Clinically significant abnormalities should be recorded on the Medical History/Adverse event eCRF page.

Symptomatic events, particularly when requiring medical intervention may lead to patient discontinuation. Treatment interruption or omitting a dose of BAF312 should be guided by the considerations outlined in [Section 6.6](#).

8.6.5 Pregnancy test and assessments of fertility

Urine pregnancy testing will be done for all female study subjects of childbearing potential at baseline and Day 30 (V11). Positive urine pregnancy tests will be confirmed with serum pregnancy testing.

Women are considered post-menopausal and not of child bearing potential if they have had 12 months of natural (spontaneous) amenorrhea with an appropriate clinical profile (e.g. age appropriate, history of vasomotor symptoms, etc.) or have had surgical bilateral oophorectomy (with or without hysterectomy), total hysterectomy, or tubal ligation at least six weeks prior to ICH. In the case of oophorectomy alone, only when the reproductive status of the woman has been confirmed by follow up FSH level assessment is she considered not of child-bearing potential.

8.7 Pharmacokinetics

Pharmacokinetic (PK) samples will be collected at the time points defined in the [Assessment schedule](#) (Section 8.1). Follow instructions outlined in the Site Operations Manual regarding sample collection, numbering, processing and shipment.

Commercially Confidential Information

As only sparse PK samples will be collected in the study, no PK parameters will be estimated. PK samples will be pooled with PK data of other available studies in order to assess the effect of various covariates on the plasma concentrations of BAF312 in patients with stroke due to ICH through a population pharmacokinetic analysis (see [Section 11.5.3](#)).

8.8 Other assessments

Commercially Confidential Information

8.9 Use of residual biological samples

Residual blood samples may be used for another protocol-specified endpoint.

Commercially Confidential Information

9 Safety monitoring

9.1 Adverse events

An adverse event (AE) is any untoward medical occurrence (i.e., any unfavorable and unintended sign [including abnormal laboratory findings], symptom or disease) in a patient after **providing written informed consent** for participation in the study until the end of study visit. Therefore, an AE may or may not be temporally or causally associated with the use of a medicinal (investigational) product.

In addition, all reports of intentional misuse and abuse of the study treatment are also considered an adverse event irrespective if a clinical event has occurred. See [Section 9.5](#) for an overview of the reporting requirements.

The occurrence of adverse events must be sought by non-directive questioning of the patient at each visit during the study. Adverse events also may be detected when they are volunteered by the patient during or between visits or through physical examination finding, laboratory test finding, or other assessments.

Abnormal laboratory values or test results constitute adverse events only if they fulfill at least one of the following criteria:

- they induce clinical signs or symptoms,
- they are considered clinically significant, or
- they require therapy.

Clinically significant abnormal laboratory values or test results should be identified through a review of values outside of normal ranges/clinically notable ranges, significant changes from baseline or the previous visit, or values which are considered to be non-typical in patients with underlying disease. Investigators have the responsibility for managing the safety of individual subject and identifying adverse events. Alert ranges for liver and kidney related events are included in [Appendix 1](#) and [Appendix 2](#), respectively.

Adverse events should be recorded on the Adverse Events CRF under the signs, symptoms or diagnosis associated with them, and accompanied by the following information:

1. CTCAE severity grade (1-5)

If CTCAE grading does not exist for an adverse event, use: 1=mild, 2=moderate, 3=severe 4=life threatening* (see [Section 9.2](#) for definition of a serious adverse event (SAE))

*Note: There may be cases where a CTCAE with a grade of 4 (life-threatening) may not necessarily be an SAE (e.g. certain laboratory abnormalities in the absence of meeting other seriousness criteria).

CTCAE grade 5 (death) is not used, but is collected as a seriousness criteria and also collected in other CRFs (e.g. Study Completion, Death/Survival).

2. Its relationship to the study treatment (no/yes).
3. Its duration (start and end dates); or if the event is ongoing, an outcome of not recovered/not resolved must be reported.
4. Whether it constitutes a SAE (see [Section 9.2](#) for definition of SAE) and which seriousness criteria have been met.
5. Action taken regarding investigational treatment. All adverse events must be treated appropriately. Treatment may include one or more of the following:
 - no action taken (e.g. further observation only)
 - investigational treatment interrupted/withdrawn
 - concomitant medication or non-drug therapy given
 - hospitalization/prolonged hospitalization (see [Section 9.2](#) for definition of SAE)
6. Its outcome (not recovered/not resolved; recovered/resolved; recovering/resolving, recovered/resolved with sequelae; fatal; or unknown).

Information about common side effects already known about the investigational drug can be found in the Investigator's Brochure (IB) or will be communicated between IB updates in the

form of Investigator Notifications. Once an adverse event is detected, it must be followed until its resolution or until it is judged to be permanent, and assessment should be made at each visit (or more frequently, if necessary) of any changes in severity, the suspected relationship to the investigational drug, the interventions required to treat it, and the outcome.

The investigator must also instruct each patient to report any new adverse event (beyond the protocol observation period) that the patient, or the patient's personal physician, believes might reasonably be related to study treatment. This information must be recorded in the investigator's source documents; however, if the AE meets the criteria of an SAE, it must be reported to Novartis.

*Refer to the Site Operations Manual for data capture methodology regarding AE collection for patients that fail screening.

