3.1 Study design

This is a randomized, patient- and investigator-blinded, placebo-controlled, parallel group study of BAF312 on top of standard-of-care for ICH, consisting of 3 *epochs*: **Screening/Baseline, Treatment, and Follow-Up** (see [Figure 3-1](#)).

Screening/Baseline Epoch

The screening/baseline epoch lasts no longer than 24 hours from the time of onset of ICH, defined as the time the patient was last witnessed to be at their normal neurological baseline, and consists of:

- The initial diagnostic neuroimaging study (CT or MRI) to determine the cause of stroke
- Obtaining informed consent
- Determining the Glasgow Coma Scale (GCS, [Appendix 6](#)) score (see [Section 20](#)) on presentation
- Obtaining medical history, including current medications
- Hospital admission laboratory studies
- Electrocardiogram (ECG)
- Pregnancy test for premenopausal female patients
- Vital signs and physical examination, including neurological examination, and

Commercially Confidential Information

Please see [Assessment schedule](#) for details.

Treatment Epoch

Patients fulfilling all eligibility criteria must be randomly allocated to one of two treatment groups in a ratio of 1:1. The treatment should start as soon as possible, ^{Commercially Confidential Information} after the time of the ICH, defined as the time the patient was last witnessed to be healthy, defined as functioning at their normal, pre-event neurological baseline.

The total treatment lasts 14 days (see [Figure 3-1](#)):

- 7 days of i.v. BAF312 with titration to the final daily dose ^{Commercially Confidential Information}

Patients must be monitored with CV telemetry or continuous bedside monitoring for the first 48 hours of i.v. BAF312 treatment. During the 7 days of i.v. infusion treatment, all patients must undergo a swallowing safety evaluation per the treating hospital's institutional guidelines and practices.

- If the patients pass a swallowing safety evaluation, the 7-day i.v. phase is followed by 7 days of CCI BAF312 p.o. QD.
- Patients who do **not** successfully pass a swallowing safety evaluation **must not** be transitioned to the p.o. phase of treatment, and BAF312 **must** be discontinued after Day 7; but they should **not** be terminated from the study. These patients should continue to be followed for the remainder of the [Assessment schedule](#).

i.v. Dose Titration

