9.2.2 SAE reporting

IMPORTANT: To comply with regulations, all suspected, unexpected, serious adverse reactions (SUSARs) occurring in a clinical trial must be reported in an expedited timeframe (7 or 15 days) to Competent Authorities.

However, regulations do allow that certain adverse experiences that would ordinarily fall under the SAE definition can be handled differently. These exemptions from reporting of SAEs are particularly relevant to studies in high morbidity and high mortality populations where study subjects are generally sicker, such as patients with ICH, and often carry significant concomitant disease burdens.

- **Event(s) common in the patient population under study:** The unblinding of single SAEs that are relatively common in the patient population under study, for SUSAR reporting, often does not increase the understanding of safety, and can damage the integrity of the blinded nature and analysis of a study. The following SAEs commonly seen in the ICH patient population will still be captured by the investigators as SAEs in the CRF and reported to Novartis, but they will not be unblinded during the course of the study, even if considered "related" to study treatment by the reporting investigator, nor reported on an expedited basis to regulatory authorities:
 1. **Ventricular extension of hemorrhage with increased ventricular pressure requiring surgical intervention (e.g., external ventricular drainage), and**
 2. **Expansion of initial intracerebral hemorrhage requiring surgical evacuation.**

Additionally, these safety data will be reviewed in an expedited timeframe of 15 days by the external DMC.

Screen Failures

Note the following requirement for Screen Failures: SAEs occurring after the patient has provided informed consent until the time the patient is deemed a Screen Failure must be reported to Novartis.

Randomized Subjects

To ensure patient safety, every SAE, regardless of causality, occurring after the patient has provided informed consent and until the study completion visit, must be reported to Novartis within 24 hours of learning of its occurrence as described below.

Any SAEs experienced after this period should only be reported to Novartis if the investigator suspects a causal relationship to study treatment.

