***On treatment:***

It corresponds to any event or any assessment occurring between the 1st study drug injection date and the last injection/intake date.

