### ***Safety profile of BAF312:***

The incidence of any treatment emergent adverse events (TEAEs), serious TEAEs overall and by severity will be summarized by treatment using frequency counts, percentages of patients and 95% Confidence Intervals (CIs) for percentages obtained using Clopper – Pearson method.

Treatment emergent adverse events are defined as any event starting or worsening on treatment (i.e. between the 1st study drug injection date and the last study drug injection/intake date).

These secondary safety endpoints will be summarized by treatment arm for the safety analysis set.

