### ECG evaluations

Standard 12-lead ECGs will be performed for all patients at screening/baseline, day 1-3, day 7. ECGs measurement HR, PR, QT, QRS, and QTcF will be listed by treatment, patient and visit/time, abnormalities will be flagged. Summary statistics of raw value and change from baseline will be provided by treatment and visit/time.

Change from baseline will only be summarized for patients with both baseline and post baseline values and will be calculated as:

$$\text{change from baseline} = \text{post baseline values} - \text{baseline value}.$$

Additionally, the number and proportion of patients with abnormal values below will be summarized:

- QT > 500 ms;
- QTcF > 500 ms;
- QTcF > 480 ms;

- QTc F > 450 ms;
- QTcF changes from baseline > 30 ms;
- QTcF changes from baseline > 30 ms and QTcF > 450 ms;
- QTcF changes from baseline > 30 ms and QTcF > 480 ms;
- QTcF changes from baseline > 30 ms and QTcF > 500 ms;
- QTc changes from baseline > 60 ms;
- QTcF changes from baseline > 60 ms and QTcF > 450 ms;
- QTcF changes from baseline > 60 ms and QTcF > 480 ms;
- QTcF changes from baseline > 60 ms and QTcF > 500 ms;
- HR decrease > 25% to a HR < 50 bpm
- HR increase > 25% to a HR > 100 bpm
- PR > 220 ms.
- PR increase > 25% to PR > 220 ms
- QRS > 120 ms
- QRS increase > 25% to QRS > 120 ms

Cardiac monitoring will be performed from 1 hour before dosing and up to 48 hours after the first drug administration. Any abnormalities in the continuous monitoring (i.e., pre-dose to 48 hours) will be reported in AE eCRF page, but will not be presented separately in listings.

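### Treatment-emergent status is set by calendar date, so an adverse event that starts before the first infusion on the same date is counted as treatment-emergent

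*Protocol*

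**What the plan says.** - **Start of collection.** Protocol 9.1 counts AEs from written consent, which precedes dosing. Protocol 9.2.2 does the same for serious events, "occurring after the patient has provided informed consent and until the study completion visit".
- **Timing data.** Protocol 9.1 item 3 asks for "Its duration (start and end dates". It does not mention clock time.
- **Treatment-emergent.** SAP 5.2.3: "Treatment emergent adverse events are defined as any event starting or worsening on treatment". The window is again stated by date, ending with the "study drug injection date and the last study drug injection/intake date". The on-treatment definition in SAP 4.4 matches it: "between the 1st study drug injection date and the last injection/intake date". Study day 1 in SAP 4.4 is the whole calendar day of the first i.v. dose.
- **Contrast.** For baseline, SAP 4.4 uses the date and time of first dose.
- **Length of the pre-dose period.** Protocol 3.1: "The screening/baseline epoch lasts no longer than 24 hours from the time of onset of ICH". Protocol 6.5 asks for prompt dosing once the patient is randomized and allows it at any hour of day or night. The outer limit for the first infusion is blacked out.
- **Telemetry.** Protocol 6.6 starts cardiac monitoring 1 h before the first dose. SAP 8.2 (ECG evaluations): "Any abnormalities in the continuous monitoring (i.e., pre-dose to 48 hours) will be reported in AE eCRF page". The SAP adds that these findings get no separate listing.

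**The concern.** A date rule works when screening lasts days or weeks, because nearly every pre-dose event then falls on an earlier date. Here the period between consent and first infusion is likely to be a matter of hours and can lie wholly within the date of first dose. On that date the rule does not separate events before the drug from events after it.

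The TEAE incidence in SAP 5.2.3, with its 95% Clopper-Pearson intervals, serves the secondary safety objective. The registry tables in SAP 8.2 also use TEAEs. The question matters most for bradyarrhythmia. It is an identified risk (protocol 1.3.1), with a heart-rate nadir about 3-4 h after first dose (protocol 3.7) and typical onset within 48 h (protocol 6.6). For such events, onset relative to the start of the infusion is key information, and monitoring deliberately begins before dosing.

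**Working it through.** The plan gives no figure on this point, so there is none to reproduce.

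**Step 1: apply the rule.** Take an AE that starts after consent and before the infusion, on the same calendar date. It is recorded, because collection starts at consent. Its start date equals the first injection date, so it lies inside the window in SAP 4.4 and 5.2.3 and is a TEAE, whether or not it worsens after dosing. If it started on the previous date and did not worsen, it is not a TEAE.

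**Step 2: share of pre-dose events caught.** Inputs:
- T, clock time of first infusion in hours after midnight. Protocol 6.5 allows any hour; uniform over 0-24 is an assumption.
- L, hours from consent to first infusion. Not given, so a range is shown.
- U, hours from event onset to infusion. Uniform over 0-L is an assumption.

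The event falls on the date of first dose when U < T, so the share is E[min(T, L)]/L. With T uniform over 24 h:
- L ≤ 24: share = 1 − (L/2)/24 = 1 − L/48. At 1 h, 1 − 1/48 = 98%; at 6 h, 1 − 6/48 = 87.5%; at 12 h, 1 − 12/48 = 75%; at 24 h, 1 − 24/48 = 50%.
- L > 24: share = 12/L. At 30 h, 40%; at 48 h, 25%.

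**Step 3: other dosing patterns.** The same expression with T uniform over a narrower band:

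| Dosing between | L = 1 h | 6 h | 12 h | 24 h |
|---|---|---|---|---|
| 00:00-24:00 | 98% | 87.5% | 75% | 50% |
| 00:00-06:00 | 92% | 50% | 25% | 12.5% |
| 00:00-12:00 | 96% | 75% | 50% | 25% |
| 08:00-20:00 | 100% | 100% | 94% | 58% |
| 12:00-24:00 | 100% | 100% | 100% | 75% |

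For example, with dosing at 00:00-06:00 and L = 12 h, mean T is 3 h and the share is 3/12 = 25%. With dosing at 08:00-20:00 and L = 12 h, one third of doses fall before noon with mean T of 10 h, so the share is 1/3 × 10/12 + 2/3 = 94%. Simulation with a million draws per cell agrees within 0.002.

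The first column also describes events in the 1 h of pre-dose telemetry, whatever the consent-to-dose interval: 92% to 100% across these patterns.

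**Step 4: effect on the comparison.** Let p1 and p0 be the true TEAE incidences and q the probability of a misclassified pre-dose event, equal in both arms and independent of later events. Each incidence becomes p + q(1 − p). The difference becomes (p1 − p0)(1 − q), and the ratio moves towards 1. The documents give no value for q.

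**Step 5: outputs affected.**
- SAP 5.2.3: any TEAE and serious TEAE, overall and by severity, and the optional relative-risk graph.
- Registry tables (SAP 8.2): TEAEs by system organ class and preferred term. The non-serious table has a threshold of incidence above 1%. One patient is 1/33 = 3.0% of an arm or 1/65 = 1.5% of the total, so one misclassified event can bring a term into the table.
- Not affected: the other AE tables in SAP 8.2, which cover all events recorded during the study, and the primary analysis of edema volume.

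**The case against.** **The AE record may hold times.** A reader might infer that AEs are recorded by date only and that the record cannot place onset before or after the infusion. The documents do not support this. Item 3 lists required content and does not exclude clock times; eCRF version 5.0, on which the SAP relies, is not among the documents. Partial-date imputation is referred to a SAP appendix that is largely blacked out. This stands, but the SAP rule would ignore an onset time even if one were recorded.

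**The interval is unknown.** A reader might also infer that consent, telemetry and infusion all fall within about 24 h, so that most pre-dose events are misclassified. The 24 h limit applies to screening/baseline from ICH onset, and the limit for the first infusion is blacked out. Even at 24 h with uniform dosing the share is only half, and with early-morning dosing it is far less. The schedule labels screening Day -1 and first treatment Day 1; events truly on an earlier date are excluded. This stands, and no single share can be claimed.

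**Few events may qualify.** Protocol 4.2 excludes heart rate below 50 bpm, sick-sinus syndrome, higher-grade AV block and PR above 220 msec. Under protocol 9.1 an abnormal test is an AE only if it causes symptoms, is clinically significant or needs therapy. Protocol 8.6.4 also allows the medical history page for telemetry findings. So a pre-dose finding does not automatically become a TEAE. This stands.

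**Other safeguards.** ECG heart rate and PR are analysed against a baseline set by date and time, relatedness is tabulated, and safety is descriptive with no test. Counting the whole first-dose date is also inclusive, which is a defensible direction of error for safety. These points limit the consequence but do not correct the TEAE tables.

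**Conclusion.** The defect is in a stated rule: as written, SAP 4.4 and 5.2.3 classify pre-dose AEs on the date of first infusion as treatment-emergent. The share of pre-dose events affected is unknown. Under uniform dosing and onset times it exceeds half for any interval below 24 h, but that rests on assumptions the documents neither confirm nor contradict. The firmest case is the telemetry hour, at 92% to 100% in the patterns examined. The number of pre-dose events is also unknown and may be small.

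A reader might suspect bias towards one arm. Allocation is randomized and blinded, so misclassification should be similar in both; the consequence is inflated rates and a diluted contrast. In SAP 5.2.3 a patient's count changes only if the pre-dose event is the only one that places the patient in that category. This is worth correcting because the rule is explicit, the remedy is small, and the same SAP section already uses date and time for baseline.

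**What to change.** In SAP 4.4 and 5.2.3, define treatment-emergent as starting or worsening at or after the date and time at which the first infusion starts. Count events with unknown onset time on that date as treatment-emergent, which keeps the inclusive direction where information is missing.

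Check the AE eCRF. If it already holds onset time, the SAP wording is enough. If not, extend protocol 9.1 item 3 and the AE page, for AEs starting on the date of first infusion only, with an onset time or a yes/no field for onset before the start of the first infusion.

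The cost is a sentence in the SAP, at most one eCRF field, and a retrospective query for patients already enrolled. Once times are available, no pre-dose event with a known time is misclassified, unless it worsens after dosing, in which case it counts correctly.
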